8.8. Dose Limiting Toxicity (DLT) Analyses

Prior to data unblinding, investigators will review AEs that occurred during the DLT-evaluation period and determine AEs that meet the DLT definition.

Dose-Determination Phase Segment 1

DLT analyses will be performed for DLT-evaluable population for patients in Dose-Determination Phase Segment 1, which include all patients who complete at least 1 cycle (4 weeks) of study treatment for segment 1 patients and have received $\geq 75\%$ of doses for both exicorilant and enzalutamide during the DLT evaluation period, or who discontinue treatment due to toxicity.

Three patient cohorts were enrolled in Dose-Determination Phase Segment 1, which are

- (1) Cohort 1: exicorilant 180mg BID/ enzalutamide 160 mg QD
- (2) Cohort 2: exicorilant 140mg BID/ enzalutamide 160 mg QD
- (3) Cohort 3: exicorilant 140mg BID/ enzalutamide 160 mg QD; No enzalutamide lead-in period

Number of patients with at least 1 DLT and number of DLTs will also be summarized by cohort, and overall.

Dose-Determination Phase Segment 2

DLT analyses will be performed for DLT-evaluable population for patients in Dose-Determination Phase Segment 2, which include all patients who complete at least 3 cycles (12 weeks) of study treatment for segment 2 patients and have received $\geq 75\%$ of doses for both exicorilant and enzalutamide during the DLT evaluation period, (or equivalently, received ≥ 63 days of doses during the first 12 weeks for segment 2 patients), or who discontinue treatment due to toxicity.

Three study regimens will be evaluated for Segment 2 Arm A during the DLT-evaluation period, which are

- (1) Regimen 1: 240 mg exicorilant + enzalutamide
- (2) Regimen 2: 240-280 mg exicorilant + enzalutamide
- (3) Regimen 3: 240-280-320 mg exicorilant + enzalutamide

DLT rate will be calculated for each study arm, study regimen and overall. The DLT rate for each study regimen is calculated as the ratio of the number of DLT-evaluable patients who experience at least one DLT during the treatment of any dose level of exicorilant from that study regimen to all DLT-evaluable patients.

One patient may experience more than one DLTs during the DLT evaluation period. Maximum Duration of DLTs will be calculated in weeks and is defined as the End Date of DLT – Start Date of DLT for the longest DLT time duration for each subject. Number of patients with at least 1 DLT, number of DLTs, and maximum duration of DLTs will be summarized by study regimen and overall.

DLT rate per patient-week will also be summarized by study arm, study regimen and overall, where the numerator is the number of patients with at least 1 DLT, and the denominator is the sum of patient's treatment duration (in weeks) during the DLT-evaluation period which is calculated as the days of the patients on treatment during the first 12 weeks divided by 7.

Number of patients with at least 1 DLT and number of DLTs will also be summarized by study arm, highest exicorilant dose level received, and overall.

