9.2 Analysis Populations and Subgroups

The following populations will be defined for this study:

- The Safety Population will include all patients who received at least 1 dose of CORT125281. All safety analyses, except evaluation of DLTs, will be based on the Safety Population.
- The DLT-Evaluable Population will include all patients in the Dose-Determination Phase cohorts who receive at least 1 dose of CORT125281 and fulfill at least 1 of the following:
 1. Complete at least the following durations of study treatment:
 - a. Segment 1: 28 days of continuous treatment with CORT125281 + enzalutamide
 - b. Segment 2: 3 cycles (≥ 84 days) of CORT125281 + enzalutamide
 2. Experience a DLT within the DLT-evaluation period (Segment 1: 28-days DLT-evaluation period; Segment 2: 3-cycles (≥ 84 -days) DLT-evaluation period).

Patients who have received $<75\%$ of the study regimen due to reasons other than toxicity or who withdraw from the study prior to completion of the DLT-evaluation period for reasons other than toxicity will be considered non-evaluable for DLTs.

- The Response-Evaluable Population (for ORR) will be the subset of the Safety Population with measurable disease at baseline and at least 1 post-baseline tumor assessment.

- The PK-Evaluable Population will be a subset of the Safety Population and will include all patients receiving active study treatment and having any measurable plasma concentration of study treatment at any time point. Prematurely discontinued patients and patients with missing sample concentrations will be included in the PK analyses provided their PK parameters can be adequately characterized based upon the remaining data.

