4.1. Primary Endpoint

This study includes a DLT endpoint to meet the primary objective of determining MTD and/or biologically active doses of exicorilant in combination with enzalutamide and to identify the RP2D.

DLTs will be recorded during the DLT-evaluation period (first dose of exicorilant through completion of Cycle 1 for Segment 1, or first dose of exicorilant through completion of Cycle 3 for Segment 2). The study protocol Section 5.5 defines a DLT as any of the following toxicities that the investigator considers possibly or probably related to study drug that occur during the DLT evaluation period:

- Hematologic DLT:
 - Grade 4 neutropenia for > 7 days.
 - Febrile Grade 3 or 4 neutropenia (absolute neutrophil count [ANC] <1000/mm³ and a single temperature of >38.3°C [101°F] or a sustained temperature of ≥38°C [100.4°F] for more than 1 hour).
 - Grade 3 thrombocytopenia with bleeding.
 - Grade 4 thrombocytopenia.
- Non-Hematologic DLT:
 - Grade 3 or greater toxicity according to National Cancer Institute Common Terminology for Adverse Events (NCI-CTCAE) v4.03 that represents at least a 2-grade increase from baseline and is not attributable to disease or disease-related processes, with the following exceptions:
 - Grade 3 fever.
 - Grade 3 fatigue, nausea, vomiting, constipation, or diarrhea that resolves to Grade 2 or less within 48 hours after standard therapy.
 - Grade 3 changes in electrolytes not associated with signs or symptoms and that resolve within 3 days off therapy. An increase in gamma-glutamyl transferase (GGT) or alkaline phosphatase alone will not be considered a DLT.
 - Transient Grade 3 increase in creatinine or dehydration lasting ≤24 hours corrected with IV fluids if needed.
 - ALT >3x ULN with concomitant total bilirubin of >2x ULN.
- Grade 2 toxicity that represents at least a 2-grade increase from baseline, which requires dose modification or delay of >1 week.
- Failure to receive >25% of the doses during the DLT period due to toxicity.
- Dose delay due to AE of greater than 2 weeks.

Occurrences of DLTs will be collected by medical operation personnel and reviewed with investigators. These data will be used for the analysis of DLTs.

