6.3. DLT Analysis Population

DLT-Evaluable Population: The DLT-Evaluable Population will include all patients in the Dose-Determination Phase cohorts who receive at least 1 dose of exicorilant and fulfill at least 1 of the following:

- Complete at least the following durations of study treatment:
 - a. Segment 1: 28 days of continuous treatment with exicorilant
 - b. Segment 2: 3 cycles (≥ 84 days) of exicorilant + enzalutamide
 - c. Have received $\geq 75\%$ of exicorilant and enzalutamide doses during the DLT-evaluation period
- Experience a DLT within the DLT-evaluation period.

Patients who have received <75% of the study regimen due to reasons other than toxicity or who withdraw from the study prior to completion of the DLT-evaluation period for reasons other than toxicity will be considered non-evaluable for DLTs.

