8.11. Interim Analyses or Timing of Analyses

The DRC consisting of Investigators, the Medical Monitor, a Clinical Pharmacologist, and additional members as appropriate will review the safety, PK, and PD data following the

completion of each cohort during Dose-Determination Phase Segment 1, after all patients have completed 3 cycles of treatment in Dose-Determination Phase Segment 2, and at least every 6 months during the Expansion Phase.

An interim safety analysis will be conducted after a total of 20 patients complete 3 cycles of therapy in the Expansion Phase. If at any time during the Expansion Phase the DLT rate exceeds 33%, the dose will be declared non-feasible, and no additional patients will be enrolled to that dose. A lower dose level may be evaluated, per the recommendation of the DRC.

9. Efficacy Analyses

The recommendations of the PCWG3 will be used to determine disease response for this study. Tumor assessments include ^{99m}Tc -methylene diphosphonate radionucleotide bone scintigraphy and CT of the chest, abdomen, and pelvis. Baseline tumor assessment will be performed within 28 days before the first dose of enzalutamide (for Dose-Determination Phase Segment 1) and/or the first dose of exicorilant (for Dose-Determination Phase Segment 2 and Expansion Phase). Post-baseline tumor assessments will be performed every 8 weeks after the first dose of enzalutamide and/or exicorilant for the first 24 weeks. Thereafter, tumor assessments will occur at intervals of 12 weeks until disease progression. Objective responses will be confirmed no less than 4 weeks after the criteria for response are first met (if possible, 4 – 6 weeks). PSA, alkaline phosphatase (ALP), and lactic dehydrogenase (LDH) will be assessed at the Baseline/Screening Visit and Day 1 of each cycle. The ITT population will be used to address the secondary and exploratory efficacy objectives of the study. Disease response and progression assessed according to RECIST v1.1 by the Investigator will provide the basis for efficacy endpoints.

At all scheduled visits, data recorded for target, non-target, and new lesions, and Investigator response assessment will be presented in by-patient listings. Summary tables and figures will be provided for endpoints as described in the following sections. Response rate endpoints will be summarized by providing the point and interval estimates. Time-to-event variables will be summarized using Kaplan-Meier estimates and plots.

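### SAP 8.8 words the DLT-evaluable population differently from SAP 6.3 and the protocol, so some patients with a DLT can fall out of the primary DLT rate; separately, the Expansion DLT rule has no stated window or denominator

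*SAP*

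**What the plan says.** **The population.** SAP 6.3 gives two ways into the DLT-Evaluable Population. One is completing the treatment duration, with a 75% dose requirement listed as item c. The other is "Experience a DLT within the DLT-evaluation period". Protocol 9.2 has the same second route, "Experience a DLT within the DLT-evaluation period (Segment 1: 28-days DLT-evaluation period", with a matching clause for Segment 2. Protocol 5.4.1 and 5.4.2 agree.

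SAP 8.8 uses the same population name but describes other members. For Segment 1 they are patients who complete a cycle with at least 75% "of doses for both exicorilant and enzalutamide during the DLT evaluation period, or who discontinue treatment due to toxicity". For Segment 2 they are patients who complete three cycles with at least 75% of both drugs, which the SAP equates to at least 63 "days of doses during the first 12 weeks for segment 2 patients), or who discontinue treatment due to toxicity". Having a DLT is not a route in for either segment.

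For Segment 2 regimens, SAP 8.8 defines the DLT rate as "the ratio of the number of DLT-evaluable patients who experience at least one DLT during the treatment of any dose level of exicorilant" of that regimen, divided by all DLT-evaluable patients. Evaluability therefore acts on both numerator and denominator. SAP Section 13 lists only the treatment-emergent and baseline definitions as changes from the protocol.

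**The Expansion rule.** SAP 8.11, like Protocol 9.8, states: "If at any time during the Expansion Phase the DLT rate exceeds 33%, the dose will be declared non-feasible". Protocol 9.2 limits the population: "The DLT-Evaluable Population will include all patients in the Dose-Determination Phase cohorts". Protocol 5.5 and SAP 4.1 give DLT-evaluation periods for Segments 1 and 2 only. SAP 6.2 excludes DLT evaluation from the analyses run on the Safety Population.

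**The concern.** The DLT endpoint is the primary endpoint. A patient who has a DLT, is held long enough to fall below 75% of doses, and then resumes is an event under 6.3 and absent under 8.8. One DLT criterion is defined by missed doses: "Failure to receive >25% of the doses during the DLT period due to toxicity". Whether that means missing more than a quarter of doses or receiving no more than a quarter, the patient is below 75%. Under 8.8 such a DLT counts only if he also stops treatment for toxicity.

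In the other direction, 8.8 admits anyone who stops for toxicity, whether or not the toxicity was a DLT. Removing events and adding non-events both push the rate down, towards a regimen that looks better tolerated. If the conflict is left until after unblinding, the choice between the two definitions would be made with the DLT data in view.

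The Expansion rule is a different defect. It closes a dose on the basis of a rate that the documents do not define for that phase.

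**Working it through.** **1. The plan's own figure.** 75% of a 12-week window is 0.75 × 84 = 63 days, which matches SAP 8.8. For Segment 1, 0.75 × 28 = 21 days.

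**2. Which single holds fall below 75%.** Fraction received = (window − hold) / window. Protocol 5.7.1 has treatment withheld and then resumed. Protocol 5.7.2 allows a hold of up to 28 days.

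| Hold | Segment 1 (28 days) | Segment 2 (84 days) |
|---|---|---|
| 7 days | 21/28 = 75.0% | 77/84 = 91.7% |
| 8 days | 20/28 = 71.4% | 76/84 = 90.5% |
| 15 days | 13/28 = 46.4% | 69/84 = 82.1% |
| 21 days | 7/28 = 25.0% | 63/84 = 75.0% |
| 22 days | 6/28 = 21.4% | 62/84 = 73.8% |
| 28 days | 0/28 = 0% | 56/84 = 66.7% |

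A patient who resumes is therefore lost under 8.8 after a hold of 8 days or more in Segment 1, and 22 to 28 days in Segment 2. When the hold is for related toxicity it is itself a DLT: more than 25% of doses missed and, beyond 14 days, a delay of more than two weeks.

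**3. Effect on the rate.** Arm A has 12 planned evaluable patients and the reference value is 33%.
- 4 DLT patients, none lost: 4/12 = 33.3%. One lost: 3/11 = 27.3%.
- 5 DLT patients, none lost: 5/12 = 41.7%. Two lost: 3/10 = 30.0%.

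**4. Sensitivity to how many are lost.** The share q of DLT patients excluded is not in the documents and is assumed here. Exact binomial probability that Arm A (12 patients before exclusions) shows a rate of at least 33%:

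| True DLT rate | q = 0 | q = 10% | q = 25% | q = 50% |
|---|---|---|---|---|
| 33% | 0.597 | 0.500 | 0.361 | 0.173 |
| 40% | 0.775 | 0.683 | 0.538 | 0.305 |

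**5. Expansion rule.** Exact probability that the observed rate exceeds 33% at some look, over 20 patients:

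| When checked | True 10% | True 15% | True 20% |
|---|---|---|---|
| After every patient, 1/3 counted as exceeding 33% | 30% | 45% | 59% |
| After every patient, more than one-third required | 22% | 35% | 49% |
| Only at 20 patients | 0.2% | 2.2% | 8.7% |

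The denominator matters too: 7 DLT patients give 7/20 = 35.0%, which triggers, but 7/24 = 29.2%, which does not.

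**The case against.** The best defence is that 8.8 names a population already defined in 6.3, consistently with the protocol, and is only a loose paraphrase. If 6.3 governs, no patient with a DLT is lost through 8.8. That reading is reasonable, but the SAP does not say which section governs, and 8.8 is where the rate is calculated.

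The affected group is also narrow. A reader might infer that every DLT patient who stays on treatment, or any who has a dose reduction, drops out. The documents do not support that. Section 8.8 counts days of dosing for Segment 2, so a reduced dose taken daily excludes no one. A DLT patient who completes the window with at least 75% of both drugs is still counted; after a one-week hold in Segment 2 he has 77/84 = 91.7%.

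The added non-events are few. Most patients who stop for related toxicity will also meet a DLT criterion. The closing sentence of 6.3 calls patients non-evaluable only for reasons other than toxicity, so 8.8 may be trying to restate that. The same sentence also pulls against the DLT route for a patient who has a DLT and then withdraws early for another reason, so the contrast with 8.8 is less clean for that group.

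Nor does 33% set the recommended dose mechanically. Under Protocol 5.4.2 the DRC weighs DLT frequency, DLT rate and overall tolerability, and at 33% or more it may consider alternatives. Protocol 1.3.2.1 shows that tolerability calls on the Segment 1 cohorts had already been made, so the Segment 1 wording mainly affects reporting.

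For Expansion, a reader might infer that tolerable doses would be closed in 30% to 59% of trials. That needs a check after every patient and 1/3 counted as exceeding 33%. The scheduled reviews are at least every six months and after 20 patients complete three cycles, although the rule's wording also covers any time. The toxicity criteria themselves exist in Protocol 5.5; what is missing is the window and the denominator.

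**Conclusion.** The point stands in this limited form. SAP 8.8 as written conflicts with SAP 6.3 and the protocol on who is evaluable for the primary endpoint, and the difference is undeclared. Taken literally it can remove a small, foreseeable group of DLT patients and add a few non-events, and both lower the rate. One lost patient is enough to move Arm A from 33.3% to 27.3%. This rests on 8.8 being followed literally and on 12 evaluable patients in Arm A. Whether any enrolled patient is affected cannot be told, because the documents do not report doses received or treatment status for the DLT patients they describe.

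The Expansion rule is a separate gap. Its DLT window, evaluable population and timing of comparison are not stated, and its chance of triggering at a true 20% rate runs from 8.7% to 59% across the readings tabulated. The documents do not show which reading is intended, so none of these figures is the rule's actual error rate.

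**What to change.** 1. In SAP 8.8, delete both restated populations and refer to 6.3.
2. State 6.3 as one rule: (completed the window and received at least 75% of both drugs) or experienced a DLT in the window. Item c then sits under completion, as in Protocol 5.4.2. Make clear that the closing non-evaluable sentence does not override the DLT route.
3. List separately the patients who stopped for a toxicity that was not a DLT.
4. If the 8.8 wording was intended, declare and justify it in Section 13 instead.
5. Reconcile Protocol 5.5, 9.2 and 9.8 with SAP 4.1, 6.3 and 8.11 so that the Expansion DLT window, denominator and timing of the 33% comparison are stated. The content of that rule is for the sponsor and the DRC.

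Items 1 to 4 are SAP wording, with no new data and no change in sample size, and should be settled before unblinding. The reported DLT rate may be slightly higher than under 8.8. Item 5 needs a short protocol clarification and a matching SAP edit.

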During the double-blind portion of the Dose-Determination Phase (ie, Segment 2), an unblinded Medical Monitor independent of the study team will provide additional oversight for the study, including review of serious unexpected AEs considered related to either CORT125281 or enzalutamide and DLTs.

The DLT-evaluation period will extend from the first dose of CORT125281 through the completion of Cycle 3. The DLT-Evaluable Population will include all patients in Segment 2 who received at least 1 dose of CORT125281 and fulfilled at least 1 of the following:

- Completed 3 cycles of treatment with CORT125281 + enzalutamide and received at least 75% of the study regimen
- Experience a DLT

Patients who are non-evaluable for DLTs will include the following:

- Received <75% of the study regimen for reasons other than toxicity
- Patients who withdraw from the study prior to completion of Cycle 3 for reasons other than toxicity (eg, lost to follow-up, withdrawal of consent, or disease progression)

Patients who are non-evaluable for DLTs will be allowed to continue in the study and receive CORT125281 in combination with enzalutamide. Patients who are non-evaluable for DLTs may be replaced to allow a sufficient number of patients to evaluate DLTs (Section 9.4.1).

After all patients complete 3 cycles of treatment or discontinue treatment, the data will be unblinded and the DRC will meet to review the safety and available PK and PD data. The DRC will evaluate the frequency of DLTs, the DLT rate (number of DLTs in DLT-evaluable patients per week [7-day period] during the DLT-evaluation period), and overall tolerability in their assessment of the dose titration regimen as the Phase 2 RD.

If the DLT rate for the regimen is $\geq 33\%$, alternative titration schemes may be considered as the regimen for the RD, such as greater time increments between dose escalations or limiting the upper range of the regimen to those dose levels corresponding to a DLT rate of $< 33\%$. Once the DRC has determined the RD, patients assigned to Arm B who have not experienced dose reductions due to toxicity will then escalate the CORT125281 dose per the recommended upward titration regimen.

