5.7.1 CORT125281 Dose Modification or Delay

If a patient experiences a toxicity of Grade 3 or greater, or an intolerable side effect, withhold enzalutamide and CORT125281 dosing for 1 week or until toxicity improves to Grade 1 or less, or to the patient's baseline. If the toxicity is attributed to CORT125281, resume CORT125281 at a reduced dose.

In Dose-Determination Phase Segment 1, the CORT125281 dose will be reduced to the next lower dose level as indicated in [Table 7](#), or at least by 25% if the dose is below Dose Level -1.

In Dose-Determination Phase Segment 2, the CORT125281 dose will be reduced in 40-mg increments from the current dose level, without unblinding the patient's treatment assignment (exceptions noted in [Section 5.12.2.1](#)), by reducing the number of capsules from the open-label bottle (the active drug) by 1 for each dose level as indicated in [Table 9](#). Additional PK assessments will be collected in all patients that have a dose reduction to enable exposure-response evaluation at the lower CORT125281 dose ([Table 21](#)).

Table 9 Dose Reductions of CORT125281 for Dose-Determination Phase Segment 2

Before Reduction ^a			First Dose Reduction ^b			Second Dose Reduction ^b		
Dose Level	No. of Capsules from Each Bottle		CORT125281 Dose	No. of Capsules from Each Bottle		CORT125281 Dose	No. of Capsules from Each Bottle	
	Open-Label	Blind-Label		Open-Label	Blind-Label		Open-Label	Blind-Label
+2	6 caps	2 caps	Prior dose – 40 mg	5 caps	2 caps	Prior dose – 40 mg	4 caps	2 caps
+1	6 caps	1 cap	Prior dose – 40 mg	5 caps	1 cap	Prior dose – 40 mg	4 caps	1 cap
1c	6 caps	0 cap	Prior dose – 40 mg	5 caps	0 cap	Prior dose – 40 mg	4 caps	0 cap

cap, capsule; No., number.

Note: The open-label bottle contains CORT125281 and blind-label bottle contains blinded capsules (CORT125281 [Arm A] or placebo [Arm B]).

^a. Reduce CORT125281 by 40 mg according to the current dose level.

^b. If a CORT125281 dose reduction is needed, the patient will have additional PK assessments ([Table 21](#)) after 14 days at the lower dose level to enable exposure-response evaluation at lower CORT125281 doses.

Once the dose has been modified for toxicity, re-escalation is not allowed.

If CORT125281 is discontinued, enzalutamide will be continued per the guidance provided in Section 5.7.1.1.

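### SAP 8.8 leaves a first Arm A DLT at a reduced dose of 200 or 160 mg out of all three Segment 2 regimen rates

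*SAP*

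**What the plan says.** SAP 8.8 states that "Three study regimens will be evaluated for Segment 2 Arm A during the DLT-evaluation period". They are "Regimen 1: 240 mg exicorilant + enzalutamide", "Regimen 2: 240-280 mg exicorilant + enzalutamide" and "Regimen 3: 240-280-320 mg exicorilant + enzalutamide". The numerator of a regimen's DLT rate is the "number of DLT-evaluable patients who experience at least one DLT during the treatment of any dose level of exicorilant from that study regimen", and the ratio runs "from that study regimen to all DLT-evaluable patients". The section does not say how a DLT on a reduced dose or during an interruption is assigned. It also does not say whether the denominator is Arm A alone or both arms.

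SAP 8.7 equates dose level with daily dose for once-daily treatment. Protocol 5.7.1 says that in Segment 2 "the CORT125281 dose will be reduced in 40-mg increments from the current dose level", shows two successive reductions from each level in Table 9, and bars re-escalation after a reduction for toxicity. The DLT-evaluation period is three 28-day cycles (Protocol 5.4.2 and 5.5).

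SAP 8.8 also plans DLT rates by arm and overall, and counts of patients with a DLT and of DLTs by the highest dose each patient received.

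**The concern.** The numerator rule works on the dose being taken when the DLT occurs. The regimens list only the doses of the upward titration, yet the protocol plans for doses below 240 mg in the same window. A patient reduced to 200 or 160 mg who then has his first DLT has failed the regimen he was on, but no regimen rate records it. Under SAP 6.3, having a DLT is itself enough to make him DLT-evaluable, so he may be in the denominator because of the very event that the numerator omits.

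The same rule has a second effect. A patient titrated to 320 mg and stepped down, who then has a DLT at 280 or 240 mg, is charged to the shorter regimens as well as to the full one. His earlier exposure to 320 mg is ignored.

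The regimen rates bear on the choice of titration scheme. If the rate reaches 33%, Protocol 5.4.2 offers as one option "limiting the upper range of the regimen to those dose levels" with a rate below 33%. The SAP's regimen percentages speak directly to that question.

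**Working it through.** The plan gives no figure that depends on the attribution rule, so there is none to reproduce. The related arithmetic in the plan is sound: 75% of 84 days is 0.75 × 84 = 63 days, as SAP 8.8 states, and 16 evaluable patients split 3:1 give 12 and 4.

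**Step 1. Doses reachable in Arm A.** Capsules are 40 mg. In Arm A the blind-label capsules are active, and each reduction removes one open-label capsule (Table 9). Dose = 40 × (open-label + blind-label capsules). The regimens charged follow from the SAP 8.8 numerator rule applied to the dose at DLT onset.

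| Dose before reduction | First reduction | Regimens charged | Second reduction | Regimens charged |
|---|---|---|---|---|
| 320 mg (6 + 2) | 40 × (5 + 2) = 280 mg | 2, 3 | 40 × (4 + 2) = 240 mg | 1, 2, 3 |
| 280 mg (6 + 1) | 40 × (5 + 1) = 240 mg | 1, 2, 3 | 40 × (4 + 1) = 200 mg | none |
| 240 mg (6 + 0) | 40 × (5 + 0) = 200 mg | none | 40 × (4 + 0) = 160 mg | none |

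Because the regimens are nested, a step-down DLT from 320 mg never leaves Regimen 3. A DLT at 200 or 160 mg leaves all three.

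**Step 2. Can the dose fall without an earlier DLT?** Yes. Protocol 5.7.1 reduces the dose for an intolerable side effect attributed to CORT125281, whereas the general Grade 2 and Grade 3 DLT criteria in Protocol 5.5 require a rise of at least two grades from baseline. An intolerable worsening from Grade 1 to Grade 2 with a short hold can lead to a reduction without being a DLT. The documents give no frequency for this.

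**Step 3. Where the 33% line falls.**
- Denominator 12: 0.33 × 12 = 3.96, so 4 patients reach it (4/12 = 33.3%) and 3 do not (3/12 = 25.0%). One patient is 1/12 = 8.3 points.
- Denominator 16: 0.33 × 16 = 5.28, so 6 patients reach it (6/16 = 37.5%) and 5 do not (5/16 = 31.3%). One patient is 1/16 = 6.3 points.

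**Step 4. Illustrations with 12 Arm A patients (assumed counts).**
- *Uncounted DLT.* Three patients have a DLT at 240 mg before any escalation, and one has his only DLT at 200 mg after a reduction from 240 mg. The SAP rule gives 3/12 = 25.0% for all three regimens. Counting every patient with a DLT, the Arm A rate is 4/12 = 33.3%. Attribution to the highest dose reached by onset gives 4/12 = 33.3% for all three regimens, in line with the arm.
- *Step-down DLT.* Three patients have a DLT at 240 mg before escalation, and one has a first DLT at 240 mg after 320, 280 and 240 mg. The SAP rule gives 4/12 = 33.3% for all three. Highest-dose attribution gives 3/12, 3/12 and 4/12 (25.0%, 25.0%, 33.3%). Regimen 3 is the same under both rules.

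**The case against.** The strongest reply is that SAP 8.8 already plans DLT counts by arm and by highest dose received. Escalation is withheld after a DLT and re-escalation after a toxicity reduction is barred, so highest dose received and highest dose up to onset should rarely differ. A DLT at 200 mg after 240 mg therefore appears in that table under 240 mg. This stands, and it limits the harm. But the table gives counts, while the percentages labelled as regimen rates follow the other rule and could disagree with it without explanation.

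A second reply is that affected patients will be few, because many toxicities that force a reduction are themselves DLTs at the higher dose. That also stands. It lowers the likelihood of the problem but does not make the rule right when it applies.

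A third is that charging step-down DLTs to lower regimens is a defensible, conservative choice, since the event did occur on that dose. This is fair, and it is why the step-down effect is secondary here. Highest-dose attribution has the opposite drawback: it can make the lower regimens look less toxic.

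A reader might infer more than the documents support:
- *That DLTs at 200 or 160 mg are lost altogether.* They are absent only from the three regimen rates. They still count in the Arm A rate, the overall rate and the highest-dose summary.
- *That the committee would decide on the regimen rates.* No section says so. Protocol 5.4.2 has it weigh DLT frequency, DLTs per week and overall tolerability, and restricting the range is optional.
- *That a DLT with onset during a hold is excluded.* The SAP is silent, so this is a gap and not a stated exclusion.
- *That the denominator is 12.* The wording fits 12 or 16.

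**Conclusion.** The point holds for the regimen rates. As written, SAP 8.8 omits a first Arm A DLT at 200 or 160 mg from every regimen numerator, including that of the full titration, while keeping the patient in the denominator. The Regimen 3 rate can then fall below the Arm A rate for the same patients. One such patient is worth 8.3 points with 12 in the denominator or 6.3 points with 16, enough to cross the 33% line in either case. Charging step-down DLTs to the lower regimens is a real but arguable consequence of the same wording, and it leaves Regimen 3 unchanged.

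This rests on reading dose level as the daily dose being taken, which SAP 8.7 supports, and on the arm rate counting every evaluable patient with a DLT. How many patients would be affected is unknown and probably small. The matter is worth correcting before unblinding; it does not undermine the Segment 2 design.

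**What to change.** Amend SAP 8.8 as follows.

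1. Attribute each patient's first DLT to the highest dose level (240, 280 or 320 mg) reached up to its onset. DLTs on reduced doses, including 200 and 160 mg, or during a hold then stay with the regimen in force before the reduction. List later DLTs in the same patient, but do not use them to add him to a lower regimen's numerator.
2. State whether the regimen denominator is the DLT-evaluable patients of Arm A only or of both arms. With an Arm A denominator, the Regimen 3 rate should equal the Arm A rate, which gives a simple programming check.
3. Apply the same attribution to the DLT rate per patient-week by regimen, for which the section gives no separate rule.
4. Show attribution by dose at onset as a sensitivity tabulation, with separate rows for 200 and 160 mg, because the primary rule can favour the lower regimens.

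The cost is a few sentences and one derived variable, close to the highest-dose variable that the SAP already needs. No new data are required and no dosing rule changes.
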